#### **Sample Size Considerations**

Due to the clinical importance of the A/H3N2 flu strain, we will focus this power analysis on the A/H3N2 strain. Between 1976 and 2007, the CDC estimates that on average three times more people died from influenza during A/H3N2-predominant seasons than in non-A/H3N2 predominant seasons (Centers for Disease and Prevention, 2010). Even the current A/H1N1 strain, which has circulated since 2009 as the pandemic 2009 A/H1N1 strain, is a less important

cause of morbidity and mortality in the elderly attributed to sustained pre-existing cross-reactive antibody titers to older strains that offer some protection (Hancock et al., 2009).

We used the criteria and comparisons proposed by FDA for a non-inferiority immunogenicity trial (FDA, 2007). They focus on changes in influenza antibody titers (our primary endpoint). The study should be adequately powered to assess the co-primary endpoints for HAI antibodies 1) post-vaccination geometric mean titer (GMT), and 2) seroconversion rates. Seroconversion is a 4-fold rise in GMT pre- to post-vaccination as long as pre-titer at least 1:10 and in pre-titer <1:10 for seroconversion the titers must achieve  $\geq 1:40$ .

To demonstrate non-inferiority in such a study:

- The upper bound of the two-sided 95% CI on the ratio of the GMTs (GMT HD vaccine/GMT Fluad) should not exceed 1.5.
- The upper bound of the two-sided 95% CI on the difference between the seroconversion rates (Seroconversion HD vaccine – Seroconversion Fluad) should not exceed 10%.

This power calculation will address both of those primary endpoints. No trials directly compare adjuvanted flu vaccine (Fluad) to HD flu vaccine or give sufficient detail in the same vaccination season to allow use of exactly the same flu strains. As a result, we must use the GMT and seroconversion data from two large trials each over 3500 subjects that compared Fluad or HD to the SD vaccine and that reported both GMT and seroconversion data (Falsey et al., 2009; Frey et al., 2014). Calculations were performed in R using the TrialSize package and power simulations were performed to confirm the results. The numbers below are the per-group sample sizes required for 80% power.

	Titer	Seroconversion
strain	analysis	analysis
H1N1	24	23
H3N2	243	144
B strain	571	168

To power the A/H3N2-specific analysis, we require 243 per vaccine group or 486 subjects total. With this sample size, we can test non-inferiority in A/H1N1 and A/H3N2 with 80% power. Assuming our observed titers are similar to those from published studies, this sample size will be sufficient to demonstrate superiority of Fluad in A/H1N1. In order to achieve this sample size, we will overenroll by 15%. This degree of over enrollment is informed by prior clinical trial experience and is expected to be adequate given the short time between blood draws and the inclusion criteria of the subjects' expectation, willingness, and ability to have the three blood draws obtained.

For the FLUBLOK pilot studies as there are not sufficient preliminary data to perform a power calculation. That is one of the key reasons why we are adding this pilot aim to prepare for future studies.

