### **Study design including population to be studied, recruitment procedures and available resources**

We propose a non-inferiority randomized clinical trial to enroll 500 Long Term Care residents age 65 and older to receive either Fluvad or HD vaccine at 1:1 ratio. Blood will be sampled pre- and post-vaccine and post-influenza season and coded for blinded laboratory analysis. The FLUBLOK pilot objective will be a substudy of the current AD Fluvad vs. HD Fluzone study (UH IRB 10-27-29), and subjects will be consented on a separate FLUBLOK ICF.

**Population:** 500 subjects age 65 and older living in long-term care facilities in Northeast Ohio area. Up to an additional 120 subjects will be added to FLUBLOK substudy.  
50:50 male:female ratio.

**Study Duration:** 3 years

**Subject Duration:** estimated 6-8 months with patient contact

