### **Analysis Plan**

The FDA guidelines (listed above) for demonstrating non-inferiority for a seasonal flu vaccine dictate the analysis of the co-primary endpoints. The ratio of the geometric mean titers will be assessed using tests of means on the log-transformed titers. The upper limit of the 95% CI of the difference (HD – Fluad) in the mean log titer will be compared to  $\log(1.5)$ . The difference in the seroconversion rates will be assessed with a two-sample proportion test. The upper limit of the 95% CI of the difference (HD – Fluad) in the seroconversion rates will be compared to 0.1. These analyses will be performed on HAI titers of all three strains obtained from studies of pre- and post vaccination serum.

For practical recruitment purposes we have to run the study over 2 years to recruit sufficient numbers of the full cohort for A/H3N2 analysis based on the sample size calculation. At the conclusion of our study, we can summarize the A/H3N2 HAI titers and seroconversion for each year separately; but our non-inferiority hypothesis is powered based on combining the years to include the total enrolment for the A/H3N2 analysis. Since we will recruit enough subjects each year due to small number of subjects needed to power the A/H1N1 analysis, we will perform and report separate analysis for each year studied as well as combining the data. For the B strain we are underpowered and will combine the two years for this exploratory result.

We will perform analyses on the other assays (NAI and SVN) on samples obtained at pre- and post- vaccination from all 3 strains. We will run HAI on all 3 strains for the post-season blood draw for Aim 1 as a secondary analysis for differences in the ability of titers to hold in one vaccine vs. the other for the length of the season. We will also run the NAI on the A/H3N2 only (for feasibility to keep assay number reasonable) on the post-season sample to assess if there are differences in maintaining anti-NA titers between the two vaccines. Any statistical tests performed for these assays are not powered to detect superiority or non-inferiority while preserving our study-wise error rate and will be considered exploratory in nature.

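### The 80% power stated for A/H3N2 is the power of the titer criterion alone; power to meet both co-primary criteria at 243 per group is about 76-79%

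*Combined protocol and SAP*

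**What the plan says.** The protocol section Sample Size Considerations sets the requirement: "The study should be adequately powered to assess the co-primary endpoints for HAI antibodies 1) post-vaccination geometric mean titer (GMT), and 2) seroconversion rates". Under what is needed to demonstrate non-inferiority it then lists two conditions, both on the upper bound of a two-sided 95% CI. The GMT ratio (HD over Fluad) must not exceed 1.5, and the seroconversion difference (HD minus Fluad) must not exceed 10 percentage points. It adds: "This power calculation will address both of those primary endpoints".

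The table that follows has one column per endpoint, introduced by: "The numbers below are the per-group sample sizes required for 80% power". For A/H3N2 the entries are 243 (titer) and 144 (seroconversion). For A/H1N1 they are 24 and 23. On method, the section says: "Calculations were performed in R using the TrialSize package and power simulations were performed to confirm the results".

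The section then adopts 243 per group, 486 in total, and states: "With this sample size, we can test non-inferiority in A/H1N1 and A/H3N2 with 80% power". The Analysis Plan section returns to the same pair of criteria: "The FDA guidelines (listed above) for demonstrating non-inferiority for a seasonal flu vaccine dictate the analysis of the co-primary endpoints". Neither section gives a power for meeting both criteria or a correlation between them.

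**The concern.** Taking the larger of two single-endpoint sizes guarantees 80% power only for the endpoint that needed it. When success requires both criteria, joint power cannot exceed the power of the weaker one. It falls below that by the probability that titer passes and seroconversion fails. At 243 per group the weaker criterion is titer, at exactly its 80% design value, so there is nothing in reserve.

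The table is open about being per endpoint. The sentence after it is not: it gives one unqualified figure for non-inferiority in A/H3N2. Since the section has just defined non-inferiority by two conditions and said that the calculation covers both, a reader would take 80% as the chance that the primary A/H3N2 claim succeeds under the planning assumptions. It is not that chance.

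**Working it through.** **Inputs from the protocol (Sample Size Considerations).** A/H3N2 sizes for 80% power: 243 for titer, 144 for seroconversion. A/H1N1: 24 and 23. Criterion: two-sided 95% CI, that is, one-sided 0.025. Chosen size: 243 evaluable per group.

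**Inputs not in the documents.** The GMTs, SDs and seroconversion rates behind the table are not listed, so 243 and 144 cannot be rebuilt from first principles and are taken as given. The correlation between the two test statistics is not given either, so it is varied.

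**Step 1: power of each criterion at n per group.** For an endpoint that needs n0 per group for 80% power, the normal approximation gives

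power(n) = Φ[(1.9600 + 0.8416) × √(n/n0) − 1.9600] = Φ[2.8016 × √(n/n0) − 1.9600].

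- Titer, n = n0 = 243: Φ(2.8016 − 1.9600) = Φ(0.8416) = 80.0%. This is the plan's stated figure.
- Seroconversion, n = 243, n0 = 144: √(243/144) = 1.2990, so Φ(3.6394 − 1.9600) = Φ(1.6794) = 95.3%.

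**Step 2: power to meet both.** With the two statistics treated as bivariate normal with correlation r, joint power is the probability that both fall on the passing side, Φ₂(0.8416, 1.6794; r). At r = 0 it is the product, 0.8000 × 0.9535 = 0.763.

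| Correlation r | Both criteria, 243 per group |
|---|---|
| 0 | 76.3% |
| 0.3 | 77.3% |
| 0.4 | 77.7% |
| 0.5 | 78.1% |
| 0.6 | 78.6% |
| 0.7 | 79.0% |
| 0.8 | 79.5% |
| 0.9 | 79.9% |

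Whatever the dependence, joint power at 243 lies between 0.8000 + 0.9535 − 1 = 75.3% and 80.0%. The lower limit needs negative dependence and is a bound, not an expectation.

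**Step 3: which correlation is plausible.** This check uses assumed inputs that are not in the documents: a two-fold HAI ladder, baseline GMT 30, SD of ln titer 1.0-1.6, pre-post correlation 0.3-0.7 and a mean rise of 2- to 8-fold. The correlation between post-vaccination log titer and seroconversion then comes out at 0.38-0.62. That corresponds to joint power of 77.6-78.7%, a loss of 1.3 to 2.4 points.

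**Step 4: sensitivity.**

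- *All enrolled subjects evaluable.* The study design section gives 500 subjects at 1:1, or 250 per group. Titer power is then 81.1% and seroconversion power 95.8%. Joint power is 77.7% at r = 0, 79.0% at r = 0.4 and 80.2% at r = 0.7.
- *Level behind the table.* If the sizes were built and tested at one-sided 0.05, seroconversion power at 243 is 94.4% and joint power is 75.5% (r = 0) to 79.3% (r = 0.8). The conclusion is the same.
- *Size for 80% joint power.* 262, 258, 254 or 249 evaluable per group at r = 0, 0.3, 0.5 or 0.7.
- *A/H1N1 at 243 per group.* 2.8016 × √(243/24) − 1.9600 = 6.95 for titer and 7.15 for seroconversion. Each power, and the lower bound on the joint power, is above 99.9%.

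**The case against.** The best defence is that no printed number is wrong. The table labels its columns by endpoint, 243 is visibly the larger A/H3N2 entry, and the sentence can be read as saying that each analysis reaches at least 80%. It gives the same 80% for A/H1N1, where actual power is close to 100%, which suggests a design threshold rather than an achieved power. That reading is possible, but it does not fit a section that defines non-inferiority by two conditions and says that its calculation addresses both. Nor does it rescue A/H3N2: if 80% is a threshold for demonstrating non-inferiority, the two-part criterion falls short of it at 243 unless the correlation is close to 1.

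Second, the plan never writes that both criteria must pass, and the Analysis Plan describes the two comparisons separately. This stands as a caveat. Even so, calling the endpoints co-primary and listing both conditions together makes that the natural reading, and nothing in the plan lets one suffice.

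Third, the effect is small beside the uncertainty of inputs borrowed from two separate trials against standard-dose vaccine. This also stands, and it is why the remedy is a sentence rather than more subjects.

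Fourth, the simulations may have covered joint success. The documents do not say. What they report as confirmed are the per-endpoint sizes, so the criticism is limited to the absence of a joint figure. The 15% over-enrollment does not fill the gap, because its stated purpose is to reach the required size, not to exceed it.

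**Conclusion.** The concern holds. At 243 evaluable per group the stated 80% is the A/H3N2 titer power. Power to meet both co-primary criteria is about 76-79% for correlations from 0 to 0.7, and probably 1 to 2 points below 80%. The result rests on three assumptions: both criteria must be met, the table was built on the plan's two-sided 95% CI, and the correlation lies in the range shown. The size of the shortfall depends on the correlation; its direction at 243 per group does not. This is a modest misstatement of the power for the analysis that sets the trial's size. It is not evidence that 243 is wrong for the titer endpoint, and it does not touch A/H1N1.

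**What to change.** In Sample Size Considerations, replace the A/H3N2 part of the power sentence with wording such as:

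> With 243 evaluable subjects per group, power for A/H3N2 is 80% for the titer criterion and about 95% for the seroconversion criterion. Power to meet both is about 76-79%, depending on their correlation.

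Alternatively, state that the 80% applies to the titer endpoint only. In either case, add a clause saying whether both criteria must be met.

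The cost is a sentence or two, with no added subjects and no design change. If the simulations generated both endpoints for the same subjects, the joint figure can be read from them and should replace the range. As an optional step, listing the GMTs, SDs and seroconversion rates assumed for each strain beside the table would let a reader check the sizes.

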### **Significance**

Data compiled by CDC in 2011-2012 showed that there were 1,383,700 residents in NHs. Also about 4,742,500 patients received services from home health agencies, and 1,244,500

patients received services from hospices, collectively accounting for much of the frailest in the US. Overall, these provider sectors served over 8 million people annually (2013). Our study will focus on residents in long term care (LTC) facilities, but the findings of our study are highly relevant to persons frail enough to require such services in all of settings where the vast majority are at least 65 years old and thus appropriate for Fludax or HD, influenza vaccines licensed for this age group.

The SD influenza vaccine has diminished efficacy in the older population with the more debilitated LTC residents being among the worst responders yet with the highest mortality. Deaths due to pneumonia and influenza and chronic lung disease were 20 times higher among NH residents compared to community residents (Menec et al., 2002). **The current availability of two vaccines specifically for the elderly that both appear to work better than SD vaccine begs the question: is the newer and less-costly Fludax vaccine non-inferior or even superior to HD vaccine?** The proposed study aims to initially address non-inferiority as this is feasible in the clinical trial R01 grant structure and a critical first step to obtain head-to-head data from the same trial, cohort and vaccine years. Our proposed study itself may provide direct guidance on vaccine usage or inform a future trial assessing actual superiority should that be appropriate based on the results of our study.

HD vaccine is increasingly used by older Americans despite its greater cost over the SD vaccine and no preferential recommendation by the Advisory Committee on Immunization Practices (ACIP), the CDC committee responsible for making the vaccine recommendations for the U.S.. A finding of non-inferiority in the primary endpoint would provide a strong rationale to consider using Fludax over HD that could result in some cost avoidance across large long-term care system in the U.S. We are not powered for a superiority analysis but in a non-inferiority trial if the findings are substantial enough they may show superiority.

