In the normal seasonal setting, influenza strains drift antigenically and therefore vary from year to year. The CDC's prediction many months before the vaccination season sets the composition for the next season's vaccine, but does not always correctly anticipate the exact strain match that eventually actually circulates. We have Medicare claims data and modeling in the NH population that there is a significant increase in death and hospitalization in bad match over good match years particularly when A/H3N2 predominates (Pop-Vicas et al., 2015). In those mismatched years in particular, heterologous immunity or immunity to other non-exact match strains becomes much more important if the vaccine is going to provide any benefit that season. Fludax is an adjuvanted vaccine that has been shown to have a more broad-based or heterologous immunity than SD vaccine that is not adjuvanted (Ansaldi et al., 2008; Frey et al., 2014). HD is also not adjuvanted. Broad based immunity is especially desirable for A/H3N2 immunity as that has had 4 different circulating strains in the last 5 years while circulating A/H1N1 has been the same for 5 years; i.e., vaccine mismatch is more likely with the A/H3N2 circulating strain. A/H3N2 is associated with the majority of influenza hospitalizations and death among the elderly (Centers for Disease and Prevention, 2010).

For the recombinant FLUBLOK arm, there is emerging data that indicates that the method of producing the vaccine may be highly clinically significant. There are important egg-induced mutations in the production process of the recent A/H3N2 strains. The egg-produced vaccines induce antibodies to A/H3N2 that have substantially less blocking ability to wild type circulating A/H3N2 than do antibodies elicited by FLUBLOK, that is produced from a wild type sequence without mutations (Zost et al). If this deleterious issue of egg-adapted mutations continues, there may be a major push in the future toward non-egg-produced vaccines such as

FLUBLOK, and away from egg-produced vaccines such as both HD and AD. This could result in a change of production methods that shy away from egg-based vaccines. This supports the need and significance for having head to head comparative studies of FLUBLOK, HD and AD.

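### Does A/H1N1 need a named deciding analysis, and do the two superiority statements conflict?

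*Combined protocol and SAP*

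**What the plan says.** The Analysis Plan applies the same two non-inferiority comparisons to the HAI titers of all three strains: log(1.5) for the mean log titer and 0.1 for seroconversion. It then describes how the two years are used, strain by strain.

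- A/H3N2: "our non-inferiority hypothesis is powered based on combining the years to include the total enrolment for the A/H3N2 analysis". Yearly results may be summarised separately.
- B strain: "For the B strain we are underpowered and will combine the two years for this exploratory result".
- A/H1N1: "we will perform and report separate analysis for each year studied as well as combining the data". The reason given is that this strain requires few participants, so either season alone should supply them.

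Sample Size Considerations gives 24 (titer) and 23 (seroconversion) per group for A/H1N1 at 80% power, against 243 and 144 for A/H3N2, and sets the trial at 243 per group, 486 in total. It says this sample size allows A/H1N1 and A/H3N2 non-inferiority to be tested with 80% power. The next sentence is "Assuming our observed titers are similar to those from published studies, this sample size will be sufficient to demonstrate superiority of Fluad in A/H1N1".

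The Significance section states: "We are not powered for a superiority analysis but in a non-inferiority trial if the findings are substantial enough they may show superiority".

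**The concern.** For two strains the reader knows which data set matters. For A/H1N1 there are three analyses on each co-primary endpoint, none is called decisive or supportive, and nothing says what happens if they disagree. The reason given for the yearly analyses is that each year has enough subjects, which could be read as allowing each season its own verdict. If a sponsor could claim A/H1N1 non-inferiority on whichever analysis succeeded, the error rate would rise. If one failed season were held against Fluad, a sound combined result could be talked down.

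The superiority wording seems to make this worse. One section says the study is not powered for superiority, and another says the sample will suffice for it in A/H1N1. The Analysis Plan defines no superiority test, so a later claim might cite the sample size text as if it had been pre-planned.

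**Working it through.** **Inputs from the documents.** Margins 1.5 (GMT ratio) and 10 points (seroconversion), both HD relative to Fluad; two-sided 95% intervals, so one-sided 0.025; 80% power; A/H1N1 sizes 24 and 23 per group; 243 per group planned; 500 subjects randomised 1:1, so 250 per arm.

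**Assumptions.** The documents do not print the seroconversion rates, GMTs or SDs taken from the two source trials. I use HD seroconversion of 20–80%, a log10 titer SD of 0.4–0.7, and an even split of 125 per arm per year.

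**1. The plan's own figures.** 2 × 243 = 486 agrees. The sizes 24 and 23 cannot be recomputed without the source data, but they can be solved backwards for the Fluad advantage they imply, with (1.960 + 0.842)² = 7.849.

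- Seroconversion: n = 7.849 × [pH(1−pH) + pF(1−pF)] / (d + 0.10)², where d = pF − pH. For pH = 0.50 and d = 0.279: 7.849 × (0.250 + 0.172) / 0.379² ≈ 23. Over pH = 0.2, 0.3, 0.5, 0.7, 0.8, d is 0.274, 0.293, 0.279, 0.214, 0.160, an advantage of 16–29 points.
- Titer: n = 2 × SD² × 7.849 / (log10 1.5 + log10 R)², where R = GMT Fluad / GMT HD. For SD = 0.5: √(2 × 0.25 × 7.849 / 24) = 0.404; 0.404 − 0.176 = 0.228; R = 1.69. Over SD 0.4–0.7, R runs from 1.4 to about 2.5.

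**2. Error if any of the three analyses could count.** Let Z1 and Z2 be independent standard normal statistics for the two years and (Z1 + Z2)/√2 the combined one. With the true difference at the margin, P(any > 1.96) = 5.8% by simulation, against 2.5% for the combined test alone; either year alone gives 1 − 0.975² = 4.9%. This is for one endpoint. Non-inferiority requires both co-primary endpoints. With both at the margin and an assumed correlation of 0.5, the figures are 1.2% for any of three and 0.46% for the combined test. The 5.8% is approached only if one endpoint lies at the margin and the other passes easily.

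**3. How often the verdicts would differ.** Seroconversion, HD rates 30–70%, yearly analyses at 125 per arm; the last two columns are simulated with 250 per arm combined.

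| True Fluad advantage | Power, one year | Power, combined (243/arm) | Three verdicts not all the same | Combined fails, a year passes |
|---|---|---|---|---|
| None | 35–41% | 60–67% | 56–58% | 6–7% |
| Quarter of implied (5–7 points) | 77–83% | 96–98% | 31–37% | 0.4–0.8% |
| Half (11–15 points) | 97–98% | above 99.9% | 4–6% | below 0.01% |
| Full (21–29 points) | above 99.9% | above 99.9% | about 0.001% or less | none seen |

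Nearly all disagreement is a combined success with a yearly failure, as expected with half the data. The selective direction is the last column. In every row Fluad truly is non-inferior, so even there a yearly success would not be a false claim.

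**4. The superiority sentence.** Power at 243 per arm is Φ(effect/SE − 1.96).

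- Seroconversion, pH = 0.50, full implied advantage: SE = √(0.422/243) = 0.0417; 0.279/0.0417 = 6.7; power above 99.9%. It stays above 99% over HD rates of 20–80%.
- Titer, SD = 0.4: SE = 0.4 × √(2/243) = 0.0363; log10 1.40 = 0.147; 0.147/0.0363 = 4.05; power 98%. It is higher for SD 0.5–0.7, and falls to 92% at SD 0.35 and 69% at SD 0.30.
- At half the implied advantage: 68–93% (seroconversion) and 53–87% (titer). At a quarter: 21–43% and 17–34%.

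Under the condition it states, the sentence is therefore supported over most of the plausible range.

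**The case for a change.** The strongest case for a change is that the plan settles the data set for A/H3N2 and B and leaves A/H1N1 open, although A/H1N1 is claimed to be powered and is not labelled exploratory. The reference to a study-wise error rate does not help, because "not powered to detect superiority or non-inferiority while preserving our study-wise error rate" describes the statistical tests on the other assays. The advantage behind 24 and 23 is taken across two separate trials, since none compared the vaccines directly. If little of it is real, disagreement between the analyses becomes common. Naming the combined analysis would cost only words, and the Significance section's remark that "circulating A/H1N1 has been the same for 5 years" gives some support for pooling.

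Part of this stands. The label is missing, the implied advantage is uncertain, and a sentence saying that the combined analysis decides would be harmless. But the text is not silent: A/H1N1 non-inferiority is tied to the sample size of 486, which exists only when the years are combined. The plan also commits to reporting the yearly and the combined results, so an unfavourable one cannot be dropped unseen. Nowhere does it say that one success among three is enough. The remark about circulating strains describes past seasons and does not show that the two study seasons will be alike, which is a reason to keep the yearly results in view.

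On superiority, the Significance section speaks of the trial as a whole and itself allows that superiority may emerge. The sample size sentence is conditional, limited to one strain, and a by-product of sizing for A/H3N2. It gives no power figure. The two can be read together.

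**Conclusion.** No change follows. The A/H1N1 point is a gap that analysts fill sensibly: the combined two-season analysis carries the conclusion, as the sample size text indicates, and the yearly analyses support it. Carrying out the plan as written produces all three results and no wrong one. The 5.8% error depends on a decision rule the plan does not contain and applies to a single endpoint; the two-endpoint figure is 1.2% even under that rule. Disagreement reaches 56–58% only if the vaccines are equal, and is about 0.001% or less at the full advantage behind the plan's own sample sizes.

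The superiority point is a mismatch of wording. Rewording either section would alter no analysis and no number, and neither 24 nor 23 is shown to be wrong. A superiority finding in A/H1N1 should be read as a by-product of a trial sized for A/H3N2.

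The magnitudes rest on assumed seroconversion rates, titer SDs, an even split between years and a correlation of 0.5 between endpoints. The reading of the text does not depend on them.
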